7.5 Exploratory Efficacy Objective

The exploratory objective is to evaluate the effect of IMR-687 versus placebo on renal function

8.0 Study Design

This is a Phase 2b, randomized, double-blind, placebo-controlled, multicenter study of subjects aged 18 to 65 years with sickle cell disease (SCD; homozygous sickle hemoglobin [HbSS], sickle- β^0 [HbS β^0] thalassemia, or sickle- β^+ [HbS β^+] thalassemia) to evaluate the safety and efficacy of the phosphodiesterase type 9 inhibitor, IMR-687, administered once daily (QD) for 52 weeks. This study will enroll approximately 99 subjects with SCD. This study consists of a screening period (up to 4 weeks), a double-blind treatment period (52 weeks), and a safety follow-up period (4 weeks).

The study schematic is provided in [Figure 1](#) below, and the schedule of assessments is provided in [Appendix 3](#) of this document.

Subjects will receive either IMR-687 (lower dose or higher dose) or placebo in a blinded fashion. IMR-687 will be supplied as 100, 150, or 200 mg white tablets. Placebo and the different doses of IMR-687 are visually identical. Subjects will be advised to take 2 tablets orally, once daily (QD). Prior to the Protocol version 4.0, lower dose was defined as an exposure of ≥ 3.0 to ≤ 4.5 mg/kg, subjects in the lower dose group weighing <67 kg will be dispensed 100 mg tablets and those weighing ≥ 67 kg will be dispensed 150 mg tablets. Higher dose was defined as an exposure of >4.5 to ≤ 6.7 mg/kg, subjects in the higher dose group weighing <67 kg will be dispensed 150 mg tablets and those weighing ≥ 67 kg will be dispensed 200 mg tablets. In Protocol version 4.0 and later, lower dose was defined as an exposure of ≥ 3.4 to ≤ 5.0 mg/kg, subjects in the lower dose group weighing <60 kg will be dispensed 100 mg tablets and those weighing ≥ 60 kg will be dispensed 150 mg tablets. Higher dose was defined as an exposure of >5.0 to ≤ 6.7 mg/kg, subjects in the higher dose group weighing <60 kg will be dispensed 150 mg tablets and those weighing ≥ 60 kg will be dispensed 200 mg tablets.

Initially, subjects will be randomly assigned in a 2:1 ratio to receive either IMR-687 lower dose or placebo. Prior to the introduction of IMR-687 higher dose, the Data Monitoring Committee (DMC) will review safety data for at least 5 subjects who received IMR-687. If the DMC recommends inclusion of the higher dose, randomization will then proceed in a 1:2:1 ratio (IMR-687 lower dose, IMR-687 higher dose, or placebo). During study conduct under Protocol Version 3.0, the DMC approved opening of enrollment to the higher dose IMR-687 group, enrollment to the higher dose went into effect on 12 March 2021.

[figure not shown]
Subjects may or may not be concomitantly receiving a stable dose of hydroxyurea (HU) according to the subject's established treatment plan. Randomization will be stratified by use of HU (yes vs. no) and by region (North America/Europe vs. Africa/Middle East).

Subjects will be directed to take study drug (either IMR-687 or placebo) with food, but if a subject does not do so, it will not be considered a protocol deviation.

An interim analysis (IA) will be conducted when all subjects have completed study assessments (including VOC incidence) at Week 24 or terminated the study early. The IA will be a partial unblinding event with corresponding alpha spending strategies to manage Type 1 error.

A final analysis (FA) will be conducted at study completion (i.e., when all subjects have reached Week 56 or terminated early), following database lock and unblinding. Alpha available at the final analysis will be propagated based on the alpha spent from the IA.

Figure 1: Overview of Study Design and Dose Groups

Abbreviation: DMC = data monitoring committee.

* Prior to the introduction of IMR-687 higher dose, the DMC will review safety data for at least 5 subjects who received IMR-687. If the DMC recommends inclusion of the higher dose, randomization across 3 dose groups will then proceed as shown.

During study conduct under Protocol Version 3.0, the DMC approved the opening of enrollment in the higher dose IMR-687 group, which went into effect on 12 March 2021.

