Furthermore, following qd dosing for 7 days in fed healthy volunteers, exposure (AUC) in healthy volunteers increased in a near dose-proportional manner (a 4.1-fold increase for a 4.5-fold change in dose [see Section 4.2.3.1]). For the higher dose arm of up to 6.7 mg/kg (assumed to be equivalent to approximately a 400 mg dose), the predicted Day 1 exposure is 32.0 $\mu\text{g}\cdot\text{h}/\text{mL}$, which is approximately 2.7-fold below the Week 39 exposure (AUC from time 0 to 24 hours [AUC_{0-24}]) in the female dog (most conservative species/gender). PK plotting (e.g., mean trough concentrations at 24 hours after study drug administration [C_{24}]) predicted that higher exposure to IMR-687 should result in drug levels above the estimated concentration at which inhibition is 90% (IC_{90}) for approximately 22 hours at a 300-mg dose and approximately 24 hours at a 400-mg dose. This possible IC_{90} advantage with respect to inhibition of the target, PDE9, further supports evaluating both the lower and higher doses of IMR-687 and specifically doses of up to 6.7 mg/kg, which can provide adequate target coverage to potentially improve clinical benefit.

This study initially imposed a minimum allowable body weight for enrollment of 45 kg and a 67-kg body weight gate for the administered tablet strength to ensure that subjects in the lower dose IMR-687 group received a dose equating to no more than the 4.5 mg/kg evaluated in the MAD part of the healthy volunteer study. Subsequently, the Data Monitoring Committee (DMC) approved the opening of enrollment in the higher dose IMR-687 group (up to 6.7 mg/kg). Having established safety and tolerability of the lower dose(s), the DMC also approved a change in body

weight gate to 60 kg and the resultant modified dose range of up to 5.0 mg/kg in the lower dose group (with the minimum weight threshold of 45 kg unchanged). Starting from Protocol Version 4.0, subjects in the IMR-687 lower dose group will receive ≥ 3.4 to ≤ 5.0 mg/kg and subjects in the higher dose group will receive >5.0 to ≤ 6.7 mg/kg; no subject will receive more than 6.7 mg/kg. Under Protocol Version 3.0, the dose ranges were ≥ 3.0 to ≤ 4.5 mg/kg in the lower dose group and >4.5 to ≤ 6.7 mg/kg in the higher dose group. Therefore, the overall dose range during the course of the study is ≥ 3.0 to ≤ 6.7 mg/kg.

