8.2. Subject Exclusion Criteria

Subjects who meet any of the following criteria will be excluded from the study:

1. Hospital discharge for sickle cell crisis or other vaso-occlusive event within the 4 days prior to randomization (Day 1).
2. Subjects participating in a chronic/prophylactic RBC transfusion program (i.e., regularly scheduled RBC transfusions); any transfusions within 21 days of screening or baseline Hb measurements.
3. Subjects with HbF >25% at screening.
4. Subjects with known active hepatitis A, hepatitis B, or hepatitis C, with active or acute event of malaria, or who are known to be positive for human immunodeficiency virus (HIV).

5. For female subjects of childbearing potential, a positive serum human chorionic gonadotropin (hCG) test (screening) or a positive urine hCG test at randomization (Day 1).
6. Significant kidney disease as indicated by, for example, estimated glomerular filtration rate (eGFR) <45 mL/min as calculated by the equation from the Modification of Diet in Renal Disease (MDRD) Study using creatinine, age, sex, and ethnicity (modified MDRD formula).
7. Alanine aminotransferase (ALT) or aspartate aminotransferase (AST) >3× the upper limit of normal.
8. Body mass index (BMI) <17.0 kg/m² or >35 kg/m²; or total body weight <45 kg.
9. Current or history of malignancies (solid tumors and hematological malignancies), unless the subject has been free of the disease (including completion of any active or adjuvant treatment for prior malignancy) for ≥5 years. However, subjects with the following history of/concurrent conditions are allowed if, in the opinion of the investigator, the condition has been adequately diagnosed and is determined to be clinically in remission, and the subject's participation in the study would not represent a safety concern:
 - a. Basal or squamous cell carcinoma of the skin
 - b. Carcinoma in situ of the cervix
 - c. Carcinoma in situ of the breast
 - d. Incidental histologic finding of prostate cancer (T1a or T1b using the tumor, nodes, metastasis clinical staging system)
10. History of a clinically significant allergic reaction or hypersensitivity, as judged by the investigator, to any drug or any component of the study drug formulations used in the study (see the IB).
11. History of unstable or deteriorating cardiac or pulmonary disease within 6 months before signing the ICF, including but not limited to the following:

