9. STUDY TREATMENTS

9.1. Study Drug

Study drug (IMR-687 or placebo) is to be taken as 2 tablets orally qd.

IMR-687 will be supplied as 100, 150, or 200 mg white tablets. To optimize dosing, 60 kg will be used as the body weight gate for the administered tablet strength. Subjects in the lower dose group weighing <60 kg will be dispensed 100 mg tablets, and those weighing \geq 60 kg will be dispensed 150 mg tablets. Subjects in the higher dose group weighing <60 kg will be dispensed 150 mg tablets and those weighing \geq 60 kg will be dispensed 200 mg tablets. The different doses of IMR-687 are visually identical in tablet form.

Placebo will be supplied as white tablets containing matrix absent IMR-687. The placebo tablets are visually identical to the IMR-687 tablets.

Subjects will be directed to take study drug (either IMR-687 or placebo) with food, but if a subject does not do so, it will not be considered a protocol deviation.

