Where specified, there will be pair-wise comparisons between IMR-687 higher dose vs placebo, IMR-687 pooled dose vs. placebo, and IMR-687 lower dose vs placebo. Of note, by study design, subjects will be randomly assigned in a 2:1 ratio to receive either IMR-687 lower dose or placebo respectively at phase one of the trial. When the DMC recommends inclusion of the higher dose, randomization will then proceed in a 1:2:1 ratio (IMR-687 lower dose, IMR-687 higher dose, or placebo), as the second phase. The placebo and lower dose from the two phases will be analyzed together without any adjustment in the statistical analysis.

The following labels will be displayed in tabulations, unless otherwise specified:

Table 6 Treatment Groups in Tabulations

| Placebo | IMR-687 200/300 mg | IMR-687 300/400 mg | IMR-687 Pooled Dose | Total |
|---------|-----------------------|-----------------------|------------------------|-------|
|---------|-----------------------|-----------------------|------------------------|-------|

The total column will only be included in the concomitant medication summaries and in the summaries pertaining to information collected before the treatment started, such as demographic, baseline and disease characteristics and prior medications.

In general, all clinical data collected from CRF, or laboratory will be stored in SDTM datasets in STDM structure and presented in subject listings.

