13.3 Exposure and Drug Accountability

A summary of exposure and compliance, to be reported on the safety analysis set, will include the total number of tablets taken, compliance (%), total exposure (mg), average daily dose (mg/day), duration of exposure (in weeks), and incidence and duration of dose interruption. These parameters will be calculated as follows:

- Duration of exposure (in weeks) will be calculated as [(date of last dose of study medication – date of first dose of study medication + 1)/7]. The date of first dose of study medication will be collected from the Study Drug Administration CRF page and the date of last dose of study medication will be collected from the End of Treatment CRF page. If there is no date for end of treatment on the End of Treatment CRF page, the last available dose date will be used. See Appendix 4 for a complete set of data handling rules.
- Total number of tablets taken = total number of tablets dispensed – total number of tablets returned. The total number of tablets dispensed and returned will be collected from study drug accountability CRF Page. They are to be collected at study visits and will be summed over the whole study treatment period.
- Total exposure (mg) of IMR-687 = Total number of tablets taken * tablet dose level (100/150/200 mg). IMR-687 will be supplied as 100, 150, or 200 mg white tablets in the study. In the lower dose group (≥ 3.0 to ≤ 4.5 mg/kg), subjects weighing <67 kg will be dispensed 100 mg tablets and those weighing ≥ 67 kg will be dispensed 150 mg tablets. In the higher dose group (4.5 to ≤ 6.7 mg/kg), subjects weighing <67 kg will be dispensed 150 mg tablets and those weighing ≥ 67 kg will be dispensed 200 mg tablets. The dose regimen for all subjects is 2 tablets once daily. The weight

at the baseline will be used to establish the dose level and the same dose level will be used throughout the trial.

- Incidence and duration of dose interruption: as collected from the IP Interruptions CRF page.
- Overall compliance (%) = [(total number of tablets dispensed – total number of tablets returned) / duration of exposure (days)] x 100.
- Average daily dose (mg/day) = total exposure (mg) / duration of therapy (days).

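### The mg/kg ranges that define the dose arms are not what the 60 kg tablet gate delivers: higher-dose subjects of 80 kg or more receive 5.0 mg/kg or less

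*SAP*

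**What the plan says.** SAP 8.0 attaches a mg/kg range to each arm. For version 4.0 and later the lower dose is 3.4 to 5.0 mg/kg inclusive. For the higher dose the text is "Higher dose was defined as an exposure of >5.0 to" 6.7 mg/kg, so its lower limit is strict. Protocol 5.1 presents these as doses delivered: "subjects in the higher dose group will receive >5.0 to" 6.7 mg/kg. It adds that "the overall dose range during the course of the study is" 3.0 to 6.7 mg/kg across protocol versions.

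The dosing rule is in Protocol 9.1: "60 kg will be used as the body weight gate for the administered tablet strength". With two tablets daily, the lower arm takes 200 mg below 60 kg and 300 mg from 60 kg. The higher arm takes 300 mg and 400 mg. Before version 4.0 the gate was 67 kg and the ranges were 3.0 to 4.5 and above 4.5 to 6.7 mg/kg (SAP 8.0).

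Exclusion 8 (Protocol 8.2) excludes BMI below 17.0 or above 35 kg/m², "or total body weight <45 kg". It sets no upper weight.

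SAP 13.3 plans to report "total exposure (mg), average daily dose (mg/day), duration of exposure (in weeks") and compliance, but not mg/kg. Its description of dispensing uses the old gate only: for the lower dose, "subjects weighing <67 kg will be dispensed 100 mg tablets and those weighing" 67 kg or more receive 150 mg tablets. SAP 13.0 introduces Table 6 with "The following labels will be displayed in tabulations, unless otherwise specified", and the labels there are 200/300 mg and 300/400 mg.

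**The concern.** A fixed tablet dose with one weight gate gives a mg/kg dose that keeps falling as weight rises above the gate. A lower limit in mg/kg can hold only if weight is capped or there is a further dose step, and the plan has neither. The stated lower limits look as if they were read off near the gate and not checked for heavier subjects.

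What is at stake is the description of the arms and any reading of results in mg/kg. Protocol 5.1 says the study will provide data over the stated range. Protocol 5.2 uses 3.4 to 6.7 mg/kg when it argues that exposures should be pharmacologically active. A report that assigned the higher-arm result to doses above 5.0 mg/kg would be untrue for some of its subjects, and no planned mg/kg table would reveal it.

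**Working it through.** **Inputs.** Daily doses of 200/300 mg (lower) and 300/400 mg (higher); gate of 60 kg for version 4.0 and later, 67 kg before (SAP 8.0, Protocol 9.1). Weight at least 45 kg and BMI at most 35 (Protocol 8.2). SAP 13.3 fixes the dose level from baseline weight for the whole trial.

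**Formula.** mg/kg = daily dose ÷ weight. The weight at which a limit L is reached is daily dose ÷ L.

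**Upper limits, version 4.0 and later: these reproduce.** Higher arm: 300/45 = 400/60 = 6.67, i.e. 6.7. Lower arm: 300/60 = 5.0.

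**Lower limits, version 4.0 and later: these do not.**

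| Arm | Weight | mg/kg | Stated lower limit |
|---|---|---|---|
| Higher | 45 to <60 kg (300 mg) | 6.67 down to just above 5.0 | >5.0, met |
| Higher | 60 to <80 kg (400 mg) | 6.67 down to just above 5.0 | >5.0, met |
| Higher | 80 kg | 400/80 = 5.00 | not met (strict) |
| Higher | 90 kg | 400/90 = 4.44 | not met |
| Lower | 59.9 kg (200 mg) | 200/59.9 = 3.34 | 3.4, not met |
| Lower | 60 to 88.2 kg (300 mg) | 5.0 down to 3.4 | met |
| Lower | 90 kg | 300/90 = 3.33 | not met |

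- Higher arm: 400/5.0 = 80 kg and 400/3.4 = 117.6 kg. From 80 to 117.6 kg the dose lies in the lower arm's range, and above that it is below both ranges. A weight of 117.6 kg is eligible only from √(117.6/35) = 1.83 m.
- Lower arm: 300/3.4 = 88.2 kg, and the dose is below 3.4 mg/kg above that. There is also a narrow band just under the gate, from 200/3.4 = 58.8 to <60 kg, most of which disappears if doses are rounded to one decimal.
- Overall floor of 3.0 mg/kg: 300/3.0 = 100 kg. It fails above 100 kg in the lower arm under either gate.
- Version 3.0 higher arm: 400/4.5 = 88.9 kg. It is at or below 4.5 mg/kg from there.

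**Are these weights eligible?** 80/1.70² gives BMI 27.7, and 80 kg is admissible at any height from √(80/35) = 1.51 m. The BMI limit at 1.70 m is 35 × 1.70² = 101.15 kg, where the lower arm gets 300/101.15 = 2.97 and the higher arm 400/101.15 = 3.95 mg/kg.

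**How many subjects?** The documents give no weight distribution. As an assumption, take a normal distribution truncated at 45 kg, with the BMI limit not applied. P(weight ≥ 80 kg) is then:

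| Mean | SD 10 kg | SD 15 kg |
|---|---|---|
| 60 kg | 2.4% | 10.8% |
| 69 kg | 13.7% | 24.5% |
| 75 kg | 30.9% | 37.8% |

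Over the same grid, P(weight > 88.2 kg) runs from 0.3% to 19.3%, P(weight ≥ 88.9 kg) from 0.2% to 18.1%, and P(weight > 100 kg) from under 0.1% to 4.9%. At mean 60 and SD 10 the 58.8 to <60 kg band holds about a further 5% of the lower arm.

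**SAP 13.3 gate.** For a subject of 60 to <67 kg under version 4.0 or later, the 67 kg text gives 200 mg where 300 mg is dispensed (1 − 200/300 = 33% low) or 300 mg where 400 mg is dispensed (1 − 300/400 = 25% low).

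**The case against.** The strongest reply is that the error is descriptive. Efficacy is analysed by randomised arm (SAP 11.4), tables are labelled in mg, and no endpoint, hypothesis or subgroup in the SAP uses mg/kg. Exposure-response work is planned on PK data. At any one weight the higher arm still receives 300/200 = 1.5 or 400/300 = 1.33 times the lower arm's dose. The version 4.0 ceilings hold, so the failures are all towards lower exposure. All of this stands, and it limits the consequence without making the stated ranges true.

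The tablet doses already appear beside the ranges in Protocol 7.1.2, and baseline weight and average daily dose will be summarised, so a reader could work out mg/kg. That is partly right. But separate summaries of weight and dose do not show how many subjects fall outside a range.

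The 38% end of the range needs a mean of 75 kg and an SD of 15 kg. The documents hint at lower means: Protocol 5.1 treats 6.7 mg/kg as about 400 mg (400/6.7 = 59.7 kg), and Protocol 5.2.2.3 puts 200 mg at about 2.9 mg/kg in the phase 2a study (200/2.9 = 69 kg). Means of 60 and 69 kg give 2.4% to 24.5%. These are reasonable anchors, though either may reflect a nominal weight, and the SDs remain assumed.

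Finally, the exposure formula in SAP 13.3 multiplies tablets by tablet strength, so it is correct if the dispensed strength is used. The 25% to 33% understatement arises only if strength is derived from baseline weight with the stale gate. The text permits that reading, because it says baseline weight establishes the dose level.

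**Conclusion.** The concern holds. The thresholds follow exactly from the documents: under version 4.0 and later the higher arm is outside its stated range from 80 kg, and the lower arm is outside its range above 88.2 kg and marginally just below 60 kg. The overall 3.0 mg/kg floor fails above 100 kg in the lower arm. Nothing elsewhere in the protocol or SAP corrects this.

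The share affected rests on the assumed weight distribution: about 2% to 38% of higher-arm subjects dosed under version 4.0 or later. Counts cannot be given, because the number started under each version is not stated. About 11 of the projected 35 lower-dose subjects (2/3 of the first 17) were randomised before the higher dose opened under version 3.0.

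The randomised comparisons with placebo and the 6.7 mg/kg ceiling are unaffected. The arm definitions, statements made in mg/kg and the gate text in SAP 13.3 should be corrected.

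**What to change.** No change of dose is proposed.

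- Define the arms by assigned tablets, 200/300 mg and 300/400 mg, as Table 6 already labels them.
- Restate, by protocol version, the mg/kg ranges that the gates give over eligible weights, including the narrow bands just under each gate, and say that the arms overlap.
- In SAP 13.3, apply the 60 kg gate for version 4.0 and later, and add baseline mg/kg by arm and protocol version to the exposure table.
- In the report, do not attribute results to the nominal mg/kg bands.

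The cost is wording in the two documents and one set of table rows from dose and baseline weight already collected. Enrolment is complete (SAP 8.1.1), so dosing and the randomised analyses stay as they are. The drawback is that the stated ranges become wider and visibly overlap.

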8.1 Sample Size and Power Considerations

8.1.1 Sample Size Determination

The sample size of this study was originally determined based on HbF responder rate as the primary endpoint:

Assuming a 5% HbF response rate for placebo, the study having approximately 31 placebo and 49 higher dose subjects would have > 85% power to detect a targeted difference of 30%, using a Chi-square test for comparison of proportions (with continuity-correction) and a two-sided alpha of 0.050. The assumed responder rate for placebo (5%) and highest tolerated dose subjects (>35%) includes the dropout subjects (regarded as are non-responders at Week 24).

Based on FDA feedback a new primary endpoint was adopted with a corresponding change in statistical methodology as specified in Section 8.1.2 below.

As of completion of this SAP, enrollment was completed in the ongoing study, with a total of 115 subjects randomized between August 2020 and August 2021. Out of the 115 subjects, the first 17 subjects were randomized in a 2:1 ratio to Lower Dose: Placebo, and the remaining 98 subjects proceeded with randomization in a 1:2:1 ratio for Lower Dose: Higher Dose: Placebo.

8.1.2 Power Estimation

Annualized rate of VOCs was changed from a key secondary endpoint in Protocol 4.0/4.1 (April 2021) to the primary efficacy endpoint in this SAP and in Protocol Amendment 5.0/5.1 (February 2022). The power calculation below was based on the projection that there will be approximately 49 randomized subjects in higher dose, 35 subjects in lower dose and 31 subjects in placebo group.

Assuming that the actual data distribution is normal when the significance level (alpha) of the test is 0.050, the standard deviation is 2.7 in both groups, and there are no dropouts, there will be 88% power to detect a difference between the medians of 5.0 and 3.0 for the placebo and the IMR-687 highest tolerated dose groups, respectively (i.e., a 40% difference), using a two-sided Wilcoxon Rank-Sum test ([Table 1](#)). Assuming a 25% dropout rate, the power will be 78%.

Table 1 Power Estimation

| Scenarios | N for IMR-687 Highest Tolerated Dose | N for Placebo | Significance Level (two-sided alpha) | Standard Deviation | Difference | Power |
|------------------------|--------------------------------------|---------------|--------------------------------------|--------------------|------------|-------|
| No Dropout | 49 | 31 | 0.05 | 2.7 | 40% | 88% |
| With 25% Dropout Rate* | 37 | 24 | 0.05 | 2.7 | 40% | 78% |

* estimated based on Ataga et al.

The power calculation for the Annualized rate of VOCs was carried out in PASS Version 2020 v20.0.3. See [Appendix 7](#) for details.

